1.2 Study Design

This is a multi-center, randomized, double blind study of approximately 50 subjects suffering from moderate to severe nasal congestion. Three sites will participate in enrollment. Those who meet the inclusion/exclusion criteria will be invited to participate in the study.

After signing an Informed Consent Form and providing Demographic Information, Medical History, Allergy History, and Medications, the subject will receive the Sonu Device (device and smartphone [if needed] and the app). Subjects will complete the Total Nasal Symptom Score (TNSS) questionnaire, Visual Analog Scale (VAS) for Headache or Facial Pain, SNOT-22 and PROMIS Sleep Disturbance Questionnaire within the App.

Subjects will be randomized to either receive treatment for two weeks, or sham therapy for two weeks. Interventional treatment arm consists of using Sonu Acoustic Resonance Therapy (ART) for 15 minutes, twice a day. Sham consists of using non-resonant acoustic energy (2 kHz, 2 seconds duration tone every 10 seconds at 50% of therapeutic volume) for 15 minutes, twice a day.

Treatment (or sham) will be completed twice daily, during a morning window from 5am to 12pm and during an evening window from 5pm to 12am. Treatments will automatically stop at 15 minutes. Subjects will complete the TNSS questionnaire and the VAS-HA/FP immediately after the second treatment each day. After the second treatment on the 7th and 14th days subjects will also complete the SNOT-22 and PROMIS questionnaire.

The Total Nasal Symptom Score (TNSS; possible score of 0-12) is a validated patient-reported outcome measure for nasal quality of life research. The TNSS is the sum of 4 symptom subdomains for rhinorrhea, nasal congestion, nasal itching, and sneezing, each self-rated by the subject using a scale of 0=None, 1=Mild, 2=Moderate, or 3=Severe. Subjects will complete the TNSS reflecting on the previous 24 hours at baseline and after the second treatment (treatment or sham), every day over the 2 week period.

The Visual Analog Scale for Headache and/or Facial Pain (VAS-HA/FP) is a measure comprised of a line where patients mark the severity of any headache or facial pain they experience, measured in a range from 0 - 100. Subjects will complete the VAS-HA/FP at baseline and after the second treatment (treatment or sham), every day over the 2 week period.

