2. STATISTICAL PLAN

The study will implement the intention-to-treat (ITT) principle, or, "analyze as randomized", which is recognized as an important protection against bias, namely balancing both known and unknown factors and eliminating selection bias. We will first compare the study subjects demographic and clinical factors to ensure the comparability between two treatment groups. For categorical variables, counts and percentages will be calculated and chi-square test or Fisher's exact test will be performed. For continuous variables, Shapiro-Wilk normality test will be performed, and either t-test or Wilcoxon rank test will be performed where appropriate. Changes in symptom scores and nasal congestion from baseline to follow-up visits will be evaluated using a paired t-test or signed rank test. Multilevel linear mixed models will be built to examine the association between treatment and outcomes. We chose this method because it handles unbalanced data and produces less biased significance than other analysis techniques- due to making use of all available data and incorporating the correlation between time points. Because there are only two time points, an unstructured correlation structure is used. The design effects include main effects of treatment group, time and the group by time interaction, while controlling for study subjects' demographic and clinical factors. We will also examine the different effect between allergic vs non-allergic rhinitis by including it as a covariate and its interaction with treatment in the models. All the analyses use a two-sided test and p<0.05 is considered to be statistically significant.

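### Allocation method and handling of site are unspecified, and site or rhinitis-type terms not crossed with time do not act on the change that defines the primary endpoint

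*Combined protocol and SAP*

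**What the plan says.** Section 1.2 Study Design describes a "randomized, double blind study of approximately 50 subjects" and states that "Three sites will participate in enrollment". Its account of allocation is one sentence: "Subjects will be randomized to either receive treatment for two weeks, or sham therapy for two weeks". It gives no ratio, block size, stratification factor or method of generating the sequence. Allergy history is listed before randomisation.

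Section 1.2 Study Endpoints defines primary effectiveness as improvement in the TNSS congestion sub-score, baseline against the daily score averaged over two weeks, Sonu versus sham. The secondary effectiveness endpoint treats total TNSS the same way.

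Section 2 says that "Multilevel linear mixed models will be built to examine the association between treatment and outcomes", with two time points and an unstructured correlation. On the terms it says: "The design effects include main effects of treatment group, time and the group by time interaction", "while controlling for study subjects' demographic and clinical factors". The factors are not listed and site is not mentioned. On rhinitis type: "We will also examine the different effect between allergic vs non-allergic rhinitis by including it as a covariate and its interaction with treatment". No crossing of that term with time is described.

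**The concern.** There are two linked gaps. First, nobody can tell from the plan whether allocation was balanced within site or rhinitis type, or whether site belongs in the model. If allocation is unstratified, a small rhinitis group or a site can end up lopsided by chance. If it is stratified by site and the model leaves site out, the standard errors are too wide and the test is conservative.

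Second, and less visibly, the terms that are planned do not do the work a reader would expect. The endpoint is a change from baseline. A covariate entered only as a main effect explains differences in level between subjects, not differences in change. The rhinitis-by-treatment term has the same problem: it compares arms on scores pooled over baseline and follow-up, whereas the question of interest is whether the improvement differs by rhinitis type.

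**Working it through.** **Inputs from the documents.** About 50 subjects, three sites, two arms, two-sided 5%, two time points in the model. The plan gives no power, effect size, SD or dropout rate, so its sample size cannot be reproduced.

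**Assumptions.** 25 per arm; sites of 17, 17 and 16; a site share s of outcome variance from 1% to 10%; 10 to 25 subjects in the smaller rhinitis type; a true effect of 0.8 SD for illustration. For scale, the effect detectable with 80% power is (1.960 + 0.842) × √(2/25) = 0.79 SD.

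**1. Which terms reach the primary contrast.** Let G be arm, R rhinitis type and S the site effect.
- Baseline: Y0 = a + bG + cR + dRG + S + e0
- Follow-up: Y1 = a + bG + cR + dRG + S + t + θG + e1
- Change: Y1 − Y0 = t + θG + (e1 − e0)

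The terms c, d and S cancel. With complete data and unstructured covariance, the estimate of θ is therefore the same with or without them. In a simulated 50-subject, three-site data set with large site differences in level, adding site as a main effect left the group-by-time estimate (−0.568) and its standard error (0.163) unchanged. Only site-by-time terms moved them. A random site intercept cancels in the same way.

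**2. Value of stratifying by site and adjusting on the right contrast.** Here s is the share of variance of the analysed outcome (change, or baseline-adjusted average), not of level. Power = Φ(0.8/√((1 − s) × 2/25) − 1.96).

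| s | Site omitted | Stratified and adjusted | Adjusted, not stratified |
|---|---|---|---|
| 1% | 80.7% | 81.1% | 79.4% |
| 5% | 80.7% | 82.7% | 81.0% |
| 10% | 80.7% | 84.6% | 83.1% |

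The gain in the third column is 0.4 to 3.9 points, worth 50s = 0.5 to 5 subjects. Using the t distribution and charging 2 degrees of freedom for site, power goes from 79.1% to between 79.5% and 83.1%, which is the same gain.

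The last column multiplies the variance by 1.0445, the mean inflation from chance imbalance over 200,000 re-randomisations with 25:25 arms. Break-even is (1 − s) × 1.0445 = 1, so s = 4.3%, or about 4% to 5% once the lost degrees of freedom are counted.

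**3. Stratified by site but site left out.** The actual level of a nominal 5% test is 2 × (1 − Φ(1.96/√(1 − s))). For s = 10% this is 3.9%.

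**4. Chance imbalance if allocation is not stratified.** With arms fixed at 25:25, the number of the smaller rhinitis type in one arm is hypergeometric.

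| Smaller type | Split counted as 2:1 or worse | Probability |
|---|---|---|
| 10 | 7:3 | 29% |
| 15 | 10:5 | 22% |
| 20 | 14:6 | 4% |
| 25 | 17:8 | 2% |

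On the same basis, at least one of the three sites splits 2:1 or worse with probability about 21%.

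**5. The rhinitis interaction, tested on the correct contrast.** SE = SD × √(sum of 1/n over the four cells). For a smaller type of 10 with balanced arms: √(1/5 + 1/5 + 1/20 + 1/20) = 0.707, so the interaction detectable with 80% power is 2.80 × 0.707 = 1.98 SD. For 15 and 25 subjects it is 1.73 and 1.58 SD. Power for an interaction of 0.8 SD is 20% to 29% when balanced and 18% to 25% at a 70:30 split.

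**The case against.** The strongest reply is that much of this is silence. A reader might infer that randomisation is not balanced on site or rhinitis type. The documents do not support that: they do not state the method, and some of the text was removed before review. The supportable finding is that the method is not specified.

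A reader might also infer that rhinitis type is missing from the model. It is not; Section 2 includes it both as a covariate and as an interaction. What remains is that, as described, it does not reach the change contrast.

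Nor does leaving out site bias the comparison of Sonu with sham. Randomisation protects that comparison, and in the stratified case the error is conservative.

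The larger imbalance figures depend on the allocation assumed. The chance that at least one site is lopsided reaches about 51% for 11:5 or worse, under simple randomisation with 16 per site. With 25:25 arms it is about 21%.

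On efficiency, the objection is also partly right. The gain is small over plausible site shares. Crossing three sites with rhinitis type gives six strata averaging about eight subjects, and leaving so small a trial unstratified can be defended. The main limit on the rhinitis interaction is the sample size, and that comparison is not a listed endpoint.

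Two replies do not succeed. Calling the model multilevel does not supply a site effect: the only correlation Section 2 describes is between time points, and a site intercept would cancel anyway. Simply adding site as a main effect to the stated model would not help the primary contrast either.

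**Conclusion.** The point holds as a gap in specification plus a modelling defect, with modest consequences. The plan does not say how subjects are allocated or how site is handled. In the two-time-point model it describes, terms not crossed with time leave the primary contrast untouched, and the rhinitis interaction does not test a difference in improvement. The cancellation is exact with complete data and needs no assumption about site variance.

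The size of the precision gain does depend on assumption, because the documents give no site variance and no enrolment by site. It is about 0.4 to 4 power points for a site share of 1% to 10% when site is both stratified and adjusted for. Without stratification, adjustment loses slightly below a share of about 4% to 5%. The risk of a lopsided rhinitis group is material only if the smaller type has about 10 to 15 subjects (22% to 29% for a 2:1 split or worse, with 25:25 arms). The documents do not give the mix. No bias in the treatment comparison follows from any of this.

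**What to change.** 1. State the allocation ratio, block scheme, stratification factors and how the sequence is generated. If enrolment has not begun, randomise 1:1 in permuted blocks stratified by site, adding rhinitis type only if the resulting strata are not too small.
2. Analyse the 2-week average congestion score, and likewise TNSS, with treatment, baseline score, site and rhinitis type as fixed effects. Site is required if randomisation was stratified by it. If the repeated-measures model is kept, cross site and rhinitis type with time so that they act on the same contrast.
3. Test rhinitis type by treatment on that contrast (in the repeated-measures form, rhinitis type by treatment by time) and label it exploratory.
4. List the remaining demographic and clinical covariates by name.
5. If enrolment has begun, leave the allocation as it is, document it, and fix the model before unblinding. If allocation was not stratified by site, adjusting for site is optional, with the small possible loss shown above.

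The cost is a new randomisation list if one can still be made, a rewritten model statement, and 2 to 3 degrees of freedom (2 for site, 1 for rhinitis type). Stratifying on both factors would also leave some blocks incomplete.

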The SNOT-22 is a validated patient-reported outcome measure for quality-of-life research, comprised of 22 questions with possible answers ranging from 0 - 5. The SNOT-22 will be collected at baseline, after week 1 of therapy or sham, and after week 2 of therapy or sham. All results will be recorded via the App.

The PROMIS Sleep Disturbance Scale is a measure that assesses the pure domain of sleep disturbance in adults 18 years and older. It consists of 8 questions with possible

answers ranging from 1 - 5. This scale will be completed at baseline, after week 1 of therapy or sham, and after week 2 of therapy or sham. All results will be recorded via the App.

At the end of the two weeks participants will be asked one question regarding their thought about which arm of the study they were randomized to.

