1.2 Study Endpoints

Safety and efficacy were evaluated by the following endpoints. Primary Endpoints.

- Primary Safety as defined as a lack of serious adverse events (SAEs).
- Primary effectiveness as defined by a statistically significant improvement in nasal congestion sub-score of TNSS, comparing baseline congestion at screening versus daily congestion averaged over 2 weeks (Sonu vs. Sham).

Secondary Endpoints

- Secondary Safety as defined as a lack of adverse events (AEs).
- Secondary effectiveness as defined by a statistically significant improvement in 24hour reflective TNSS comparing baseline TNSS at screening versus daily TNSS averaged over 2 weeks (Sonu vs. Sham).

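### The allergic v non-allergic analysis names rhinitis-by-treatment, which is not the subtype difference in treatment effect when baseline is one of the two time points

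*Combined protocol and SAP*

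**What the plan says.** Section 2 (Statistical Plan) specifies multilevel linear mixed models: "The design effects include main effects of treatment group, time and the group by time interaction", with adjustment for subject characteristics. On covariance it says: "Because there are only two time points, an unstructured correlation structure is used". It does not say which two time points these are. It then proposes to look for different effects in "allergic vs non-allergic rhinitis by including it as a covariate and its interaction with treatment in the models". No rhinitis-by-time term and no rhinitis-by-group-by-time term is named, and the coefficient to be tested is not identified.

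Section 1.2 Study Endpoints defines primary effectiveness on the congestion item by "comparing baseline congestion at screening versus daily congestion averaged over 2 weeks (Sonu vs. Sham", and the secondary TNSS endpoint is defined in the same way. Section 2 also refers to "Changes in symptom scores and nasal congestion from baseline to follow-up visits", although that phrase belongs to the sentence on paired tests, not to the mixed model.

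The other questionnaires follow a different schedule. Section 1.2 Study Design states: "The SNOT-22 will be collected at baseline, after week 1 of therapy or sham, and after week 2 of therapy or sham", and PROMIS is collected at the same times. These have three time points and are outside this point.

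**The concern.** If the two rows per subject are baseline and the two-week average, randomisation makes the expected arm difference zero at baseline. The treatment effect is then the group-by-time coefficient. A treatment effect that differs between allergic and non-allergic subjects is a difference in that coefficient, which is the three-way term.

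A rhinitis-by-treatment term without time is a single number applied to both rows. It blends the subtype contrast at baseline, where nothing is expected, with the contrast at follow-up, where any real difference lies. The reported interaction is then the subtype difference multiplied by a weight set by the variances and the correlation. A real difference could be reported at a fraction of its size and read as similar benefit in both types.

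The opposite slip is also possible. If the analyst adds the three-way term but still reports the two-way coefficient with baseline coded 0, that coefficient is the baseline difference only.

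This is the only subgroup question in the plan.

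**Working it through.** The plan gives no figure for this analysis to reproduce. It gives about 50 subjects, two time points, an unstructured covariance and a two-sided 0.05 level. The SDs, the correlation, the subtype split and the size of any subtype difference are all assumptions.

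**Weight.** Let c0 and c1 be the subtype-by-arm contrasts (Sonu minus sham in allergic subjects, less the same in non-allergic subjects) at baseline and follow-up. Under randomisation E(c0) = 0; let E(c1) = d. With baseline SD s0, follow-up SD s1 and correlation r, the variances of c0 and c1 and their covariance are proportional to s0², s1² and r·s0·s1. A model that forces one value on both rows returns their minimum-variance weighted average, so the two-way term has expectation w·d, where

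w = (s0² − r·s0·s1) / D, with D = s0² + s1² − 2·r·s0·s1.

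The three-way term is c1 − c0, with expectation d. The weight w does not depend on the subtype split. It is negative if s0 < r·s1, and is 1 or more if s1 ≤ r·s0.

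**Standard errors** with n per arm-by-subtype cell:
- two-way: √[(4/n)·s0²·s1²·(1 − r²)/D]
- three-way: √[(4/n)·D]

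**Worked case:** s0 = 0.5, s1 = 0.6, r = 0.4, n = 13, d = 0.6.
- D = 0.25 + 0.36 − 0.24 = 0.37; w = (0.25 − 0.12)/0.37 = 0.351.
- Two-way estimate: 0.351 × 0.6 = 0.211; SE = √[(4/13) × 0.25 × 0.36 × 0.84/0.37] = 0.251.
- Three-way estimate: 0.600; SE = √[(4/13) × 0.37] = 0.337.

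Generalised least squares with the covariance treated as known gives the same values. Below, r = 0.4, n = 13 and d = 0.6 throughout. Power is Φ(z − 1.96) + Φ(−z − 1.96), with z = estimate/SE.

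| s0 / s1 | w | Two-way (SE) | Three-way (SE) | Power, two-way v three-way |
|---|---|---|---|---|
| 0.45 / 0.6 | 0.27 | 0.164 (0.233) | 0.600 (0.327) | 11% v 45% |
| 0.5 / 0.6 | 0.35 | 0.211 (0.251) | 0.600 (0.337) | 13% v 43% |
| 0.6 / 0.6 | 0.50 | 0.300 (0.278) | 0.600 (0.365) | 19% v 38% |
| 0.7 / 0.5 | 0.76 | 0.457 (0.262) | 0.600 (0.376) | 41% v 36% |

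With a 75/25 subtype split of 52 subjects, the two-way estimates are unchanged. Power at 0.5/0.6 is then 11% (two-way), 34% (three-way) and 40% (baseline-adjusted).

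**Range of w.**
- Both SDs in 0.45–0.70, r = 0.3–0.5: 12% to 88%. The low end is (0.2025 − 0.1575)/0.3775 = 0.119.
- Extremes at r = 0.6: SDs 0.4/0.7 give (0.16 − 0.168)/0.314 = −2.5%; SDs 0.7/0.4 give (0.49 − 0.168)/0.314 = 102.5%.
- The trial enrols "approximately 50 subjects suffering from moderate to severe nasal congestion", and the item is "each self-rated by the subject using a scale of 0=None, 1=Mild, 2=Moderate, or 3=Severe". If eligibility used this item, baseline takes only the values 2 and 3, and its SD is at most about √(0.5 × 0.5) = 0.5. With s0 = 0.40–0.50 and r = 0.3–0.5, w is 5% to 50% for s1 = 0.50–0.70, and up to 71% (0.15/0.21) if s1 falls to 0.40.

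**Simulation.** Four settings of 2,000 runs each: 50 subjects, baseline 2 or 3 (30% or 50% severe), follow-up the mean of 14 daily 0–3 scores (s1 about 0.59, r about 0.36–0.39), 52% or 76% allergic, covariance estimated. With a true subtype difference of 0.56–0.58:
- The two-way term averaged 0.17–0.22, or 31–39% of the truth; the three-way and baseline-adjusted terms averaged 0.56–0.58.
- Power was 11–15% (two-way), 29–37% (three-way) and 34–43% (baseline-adjusted).
- With no subtype difference, the two-way term rejected in 4.4–6.9% of runs.

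**The case against.** The strongest reply is that this is loose wording, not an error. The sentence states its aim, a different effect by rhinitis type, directly after the model has been defined through group-by-time. In a one-paragraph plan, interaction with treatment may simply mean interaction with whichever term carries the treatment effect. The text does not exclude that reading, and if it was intended only a clarification is needed.

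Other readings would also make the two-way term right. It is correct for change scores or for follow-up adjusted for baseline. It is a legitimate average difference if the two time points are weeks 1 and 2, with the baseline score among the covariates. The first two do not match a model with time and group-by-time effects. The third would suit SNOT-22 and PROMIS, but fits poorly with congestion and TNSS endpoints defined as baseline against a two-week average.

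The objection that the size is unknown stands. Every SD, correlation and subtype difference is assumed, and the possible range of w is wide. Power is not the main argument either: in the 0.7/0.5 row the two-way term has more of it, and even the right coefficient is weakly powered at about 50 subjects. Finally, the upper simulated rejection rate of 6.9% exceeds 5% by more than simulation error, which is about √(0.05 × 0.95/2000) = 0.5 points. Type I error is close to nominal, but not exactly so.

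**Conclusion.** The concern holds, as a minor point. If the two rows are baseline and the two-week average, the rule as written estimates w times the subtype difference, and equals that difference only in the special case s1 = r·s0. The distortion cannot be fixed from the documents. It is half with equal SDs, and larger when follow-up is more variable than baseline, as it may well be if entry limits the baseline score to 2 or 3.

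The overall group-by-time test is not affected. The subgroup analysis is not an endpoint and is best treated as exploratory, although the plan does not label it so. What is at stake is whether the reported interaction can be read as a difference in benefit. Confidence is medium, because the plan leaves the two time points unstated and the wording may be shorthand.

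**What to change.** In Section 2, state the two time points for congestion and TNSS and name the tested coefficient, choosing one of:

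- rhinitis-by-treatment-by-time in the same two-time-point model, with all lower-order terms, including rhinitis-by-time; or
- rhinitis-by-treatment in a model for the follow-up score adjusted for the baseline score.

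State which is used, report the Sonu-minus-sham effect with its 95% CI in each subtype, and label the analysis exploratory. If the three-way term was already meant, one clarifying sentence is enough.

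No extra data are needed. The three-way option adds two model terms, and in the four tabulated settings its standard error is 31% to 44% larger than that of the two-way term, so it can lose power. The baseline-adjusted option had higher power than the three-way term in the simulated settings, but it is a different model from the main group-by-time analysis, so subtype and overall effects would not come from one fit.

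### Total TNSS has its own success criterion at p<0.05 that does not depend on the congestion result, so secondary effectiveness could be declared after the primary fails

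*Combined protocol and SAP*

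**What the plan says.** The section headed Study Endpoints in the combined protocol and SAP names one primary and one secondary effectiveness endpoint, and states each as a criterion for success:

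- "Primary effectiveness as defined by a statistically significant improvement in nasal congestion sub-score of TNSS"
- "Secondary effectiveness as defined by a statistically significant improvement in 24hour reflective TNSS"

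Both compare baseline with the daily scores averaged over two weeks, Sonu against sham. The Study Design section shows how the two are related: "The TNSS is the sum of 4 symptom subdomains for rhinorrhea, nasal congestion, nasal itching, and sneezing". Congestion is therefore one of the four items in the secondary endpoint.

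Section 2, Statistical Plan, has a single decision rule: "All the analyses use a two-sided test and p<0.05 is considered to be statistically significant". The same section plans within-group tests ("Changes in symptom scores and nasal congestion from baseline to follow-up visits will be evaluated using a paired t-test or signed rank test") and an interaction between treatment and rhinitis type. Nowhere do the documents give a testing order, a split of alpha or any other control for multiplicity, and nowhere do they say whether the secondary claim depends on the primary result.

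**The concern.** The secondary endpoint is more than a descriptive measure. It has its own definition of success, and the 0.05 rule applies to it without condition. Suppose congestion misses significance and TNSS gives p = 0.04. Read literally, the plan then says that secondary effectiveness has been met. The Objectives section sets the trial the task of demonstrating effectiveness, so such a result could be put forward as a demonstrated effect. The 5% level attached to the primary test does not cover a claim reached by that route.

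The labels primary and secondary rank the endpoints by importance. They do not make one test conditional on the other. Without a written rule, the standing of a lone TNSS success would be settled after the data are known.

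**Working it through.** The documents state no familywise error rate, so there is no figure of the plan's own to reproduce. The question is what two tests at 0.05 imply.

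**Inputs from the documents**
- Significance level: two-sided 0.05 for each analysis (Statistical Plan), so the critical value is 1.96.
- Two effectiveness tests, each requiring an improvement over sham (Study Endpoints).
- Congestion is one of four items summed in the TNSS (Study Design), so the two test statistics should be positively correlated.

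**Input that is assumed**
- The correlation ρ between the two test statistics. If the four items have equal variance and a common inter-item correlation r, the correlation of one item with the total is (1 + 3r)/√(4 + 12r) = √(1 + 3r)/2. This gives 0.50 at r = 0, 0.69 at r = 0.3, 0.79 at r = 0.5 and 0.88 at r = 0.7. The range used is 0.5 to 0.9. Unequal item variances could put ρ below 0.5, so independence is shown as the limit.

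**Formulas**, with no true effect on either endpoint and (Z1, Z2) bivariate normal with correlation ρ:
- At least one rejection in either direction: 1 − P(|Z1| ≤ 1.96 and |Z2| ≤ 1.96). At ρ = 0 this is 1 − 0.95² = 9.75%.
- At least one false finding of benefit: 1 − P(Z1 ≤ 1.96 and Z2 ≤ 1.96). At ρ = 0 this is 1 − 0.975² = 4.94%.

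**Results**

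| ρ | Two-sided | Excess over 5% | Benefit direction | Excess over 2.5% |
|---|---|---|---|---|
| 0 (limit) | 9.75% | 4.75% | 4.94% | 2.44% |
| 0.5 | 9.07% | 4.07% | 4.54% | 2.04% |
| 0.7 | 8.35% | 3.35% | 4.17% | 1.67% |
| 0.8 | 7.81% | 2.81% | 3.90% | 1.40% |
| 0.9 | 7.04% | 2.04% | 3.52% | 1.02% |

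Each excess is the error rate minus that of the primary test alone. It is therefore the probability that TNSS rejects when congestion does not. In the benefit direction, the route left open adds about 1 to 2 percentage points. The relative inflation is 7.04/5 = 1.4 to 9.07/5 = 1.8, and is the same for benefit (3.52/2.5 = 1.4 to 4.54/2.5 = 1.8).

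**After the fix.** If TNSS is tested only after congestion succeeds, no claim can be made unless the first test rejects. With no effect on either endpoint, the familywise error is at most 5% two-sided and 2.5% towards benefit, whatever ρ is. Splitting alpha at 0.025 each would also hold it (1 − 0.975² = 4.94% if independent), but would take power from the primary.

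**The case against.** The strongest reply is that the endpoints are already ranked. There is one named primary with one test, and its error is 5% two-sided whatever happens to TNSS. The objective concerns patients with nasal congestion, which is what the primary measures, and no sentence says that TNSS alone would meet it. All of this stands. It confines the problem to the secondary claim but does not remove it, because that claim has an unconditional success definition and the documents do not say what a lone TNSS success would mean.

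Three stronger readings are tempting, and the documents do not support them.

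- A reader might infer that the chance of a false effectiveness claim is 8% to 10%. Rates of that size are two-sided and also count significant results in favour of sham, whereas both endpoints require improvement. The top of that range also needs nearly uncorrelated tests, which is implausible when one endpoint is an item of the other.
- A reader might count every collected score. Five independent tests (congestion, TNSS, the headache and facial pain scale, SNOT-22, PROMIS) would give 1 − 0.95⁵ = 22.6%. Study Endpoints lists only the first two as effectiveness endpoints. The rule in the Statistical Plan says when a p-value is called significant; it does not turn each significant p-value into an effectiveness claim. The same holds for the within-group tests and the rhinitis interaction.
- A reader might conclude that significance statements for those other analyses must be barred. That would be a reporting preference. Labelling them exploratory is enough.

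**Conclusion.** The concern holds for the secondary effectiveness claim. As written, total TNSS can be declared a success after congestion has failed, and nothing controls the error over the two claims together. That error is about 7% to 9% two-sided, or 3.5% to 4.5% towards benefit, against 5% and 2.5% for a single test. The figures assume no true effect on either endpoint, approximately normal test statistics and correlations of 0.9 to 0.5. Independence (9.75% and 4.9%) is only an upper bound for non-negative correlation. The primary test and its error rate are not affected. This is a cheap improvement to the plan; the primary conclusion does not depend on it.

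**What to change.** Add to the Statistical Plan, before unblinding, wording such as:

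> The Sonu–sham comparison of the congestion item is tested first at two-sided 0.05. Total TNSS is tested at two-sided 0.05 for the secondary effectiveness claim only if the congestion result is significant in favour of Sonu. All other analyses are exploratory and support no effectiveness claim.

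In Study Endpoints, state that the secondary effectiveness definition applies subject to this order.

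The cost is a short addition to the text. The primary is still tested at the full 0.05, so its power is unchanged and no extra subjects are needed. The downside is that if congestion fails, a significant TNSS result may be reported but not claimed as effectiveness.
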